# III. Research design

- 1. This study is a prospective, nonrandomized, open-label, single-arm clinical trial. The sirolimus capsule (Rapamycin, Yixinke®), 0.5 mg/grain\*20/box, is produced by North China Pharmaceutical Co., Ltd.
- 2. All patients who meet inclusion criteria and sign informed consents receive sirolimus treatment for at least 6 months. Patients are followed up remotely in a regular schedule.
- 3. No less than 10 patients should be enrolled.

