### D. Rejection criteria

- (1) Patients who violate the requirements of the test protocol
- (2) Patients with poor-recording, incomplete, or inaccurate data

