#### C. Adults' dosage regimen

1) Initial dose and dosing schedule: sirolimus 2mg, once a day. Maintain drug trough concentration of 5-10ng / mL in blood. If adverse events are too severe to tolerate, daily dosage can be reduced by 0.5mg every week. The minimum dosage is 1 mg/day. If patient still cannot tolerate minimum dosage, withdraw from the study. If patient could tolerate the possible adverse events, continue to take the original dose for 3 months, and evaluate improvement of disease condition.

2) Subsequent dose and dosing schedule: After taking sirolimus 2 mg once a day for 3 months, those with improved condition continue to take the original dose. If improvement of disease condition is not obvious, change dosage to 2.5mg-3mg once a day. If this dosage cannot be tolerated, patients may withdraw from the study. If it can be tolerated, continue to take sirolimus for another 3 months and reassess the improvement of condition.

3) Blood drug concentration test: Blood samples are taken at 1st month, 3rd months, and 6th months of dosage schedules.

4) Iron supplementation: For subjects with hemoglobin  $\leq 10.9$  g / dl, iron supplementation should be provided according to the standard dosing regimen, but iron supplementation is not considered as study treatment and will be recorded as concomitant medication.

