### B. Evaluation during sirolimus treatment

Adverse reactions are evaluated weekly during the first month of drug treatment. The efficacy and safety are then evaluated at the 3rd and 6th months, and the contents of the examination is the same as the pre-trial evaluation.

1) Efficacy assessment:

a. Clinical symptom assessment (including ileus, VAS pain score, gastrointestinal bleeding and some other related symptoms);

b. Changes in hemoglobin;

c. Nutritional status (including albumin, etc.);

d. Abdominal and pelvic cavity contrast-enhanced CT + small intestine reconstruction CT examination, digestive system endoscopy to measure the size, quantity and total load of intestinal polyps;

e. (For patients with secondary malignant tumor) Tumor response to the drug, such as changes of tumor marker, tumor regression shown by imaging, metastasis and etc.

2) Safety assessment: Safety parameters (such as asking adverse events, measuring laboratory values, vital signs, gastrointestinal bleeding, etc.) will be closely monitored on a regular basis throughout the study.

3) Treatment compliance: In order to monitor compliance, subjects are required to complete an electronic diary during the entire study period. Dates of drug intake will be tracked by this diary. At every visit, the investigator and the subject will review the integrity of the electronic diary data together.

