#### **C.** Evaluation after treatment

Evaluation of curative effects and safety is conducted at the end of the drug therapy, six and twelve months after the treatment. Its content is the same as pre-trial evaluation.

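### The month-3 dose increase opens a study exit only to adults without obvious improvement, so later efficacy readings can be lost selectively

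*Combined protocol and SAP*

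**What the plan says.** Section III makes this an open-label, single-arm trial with a minimum of 10 patients, and sets the treatment period: "All patients who meet inclusion criteria and sign informed consents receive sirolimus treatment for at least 6 months".

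Section V.C item 2 divides adults by response after 3 months on 2 mg. Those who have improved keep their dose. For the others: "If improvement of disease condition is not obvious, change dosage to 2.5mg-3mg once a day". Two sentences cover what follows the increase: "If this dosage cannot be tolerated, patients may withdraw from the study", and "If it can be tolerated, continue to take sirolimus for another 3 months and reassess the improvement of condition". Item 1 has an earlier exit that depends on toxicity, not response: "If patient still cannot tolerate minimum dosage, withdraw from the study".

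On efficacy visits during treatment, section VI.B says "The efficacy and safety are then evaluated at the 3rd and 6th months". Section VI.C adds "Evaluation of curative effects and safety is conducted at the end of the drug therapy, six and twelve months after the treatment". Section IV.D item 2 lists for rejection "Patients with poor-recording, incomplete, or inaccurate data", without saying from what. Section VIII.B bases efficacy on follow-up and re-examination findings. Section VIII defines no analysis set and gives no rule for patients who leave.

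**The concern.** Item 2 does not separate stopping the drug from leaving follow-up. The exit it creates can be reached only by adults already classed at month 3 as not obviously improved. Improvers never meet it, although the general exits in section IV.C apply to everyone.

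Efficacy here is judged by change within patients, and no control arm would reveal a selective loss. Suppose escalated non-improvers leave, are not measured again and are dropped as incomplete. The month-6 and off-drug results would then describe a group with fewer poor early responders than the group treated. If the leavers would have done worse than those who stayed, the drug looks better than it is.

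**Working it through.** **1. Does any text close the gap?**

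| Section | What it provides | Does it cover an item 2 leaver? |
|---|---|---|
| V.C item 2 | Reassessment after 3 more months | Stated only for those who tolerate 2.5-3 mg |
| VI.B | Efficacy at months 3 and 6 | Month 3 comes before the increase, so it is not lost by this route; month 6 falls under evaluation during treatment |
| VI.C | Evaluations when therapy ends and 6 and 12 months later | Can be read to include early stoppers; does not say it applies after leaving the study |
| VII.F item 4 | Tracking of adverse events to resolution | Yes, but for safety only |
| IV.D item 2 | Rejection for incomplete data | Could remove the whole patient, month 3 included |
| VIII.B | Efficacy from follow-up results | Silent on leavers |

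The loss is possible under the plan as written, but not certain.

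**2. How large could it be?** The plan gives no response rate, intolerance rate or dropout figure, so there is nothing of its own to reproduce. The share improved at month 6 is used only for illustration; the plan does not name it as an endpoint.

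Inputs: N = 10 (section III minimum); 4 patients without obvious improvement at month 3 (assumed); a and b = share improved at month 6 among month-3 improvers and non-improvers (assumed); L = number leaving by this route, with leavers sharing b.

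- All enrolled = (6a + 4b)/10
- Completers = (6a + (4 − L)b)/(10 − L)
- Overstatement = completers − all enrolled

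Example, a = 0.8, b = 0.5, L = 2: all enrolled = (4.8 + 2.0)/10 = 68.0%; completers = (4.8 + 1.0)/8 = 72.5%; overstatement +4.5 points.

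| a, b | All enrolled | L = 1 | L = 2 | L = 3 | L = 4 |
|---|---|---|---|---|---|
| 1.0, 0 (extreme) | 60% | +6.7 | +15.0 | +25.7 | +40.0 |
| 0.8, 0.5 (moderate) | 68% | +2.0 | +4.5 | +7.7 | +12.0 |
| 0.8, 0.8 (equal) | 80% | 0 | 0 | 0 | 0 |
| 0.6, 0.8 (non-improvers do better) | 68% | −1.3 | −3.0 | −5.1 | −8.0 |

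Now let L follow a Binomial(4, q) distribution, where q is an assumed chance that an escalated patient is intolerant and leaves. Then P(L = 0) = (1 − q)^4, and the mean overstatement averages the row above over L (L = 0 gives 0).

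| q | P(nobody leaves) | Extreme | Moderate | Equal | Non-improvers do better |
|---|---|---|---|---|---|
| 5% | 81% | +1.4 | +0.4 | 0 | −0.27 |
| 10% | 66% | +2.8 | +0.8 | 0 | −0.55 |
| 25% | 32% | +7.3 | +2.2 | 0 | −1.47 |
| 50% | 6% | +16.2 | +4.9 | 0 | −3.24 |

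**3. Against sampling error.** The exact 95% interval for 6/10 is 26.2% to 87.8%. The moderate-case shifts are small beside it.

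**4. Would counting leavers as not improved solve it?** On average 4q patients leave, and a share b of them would have improved, so the mean error is −4qb/10. At b = 0.5 this is −2.0, −5.0 and −10.0 points for q = 10%, 25% and 50%. Each is larger than the moderate-case bias it is meant to correct (+0.8, +2.2, +4.9).

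**The case against.** A long chain of conditions must hold. An adult must be not obviously improved at month 3, fail to tolerate a step that may be only 0.5 mg above a dose already taken for 3 months, choose an exit that is optional, have no usable end-of-therapy evaluation, be dropped from the analysis, and do worse than those who stay. Returning to 2 mg is not forbidden, and such a patient would be measured at month 6. Item 1 allows weekly 0.5 mg reductions, though it is arguable whether that reaches item 2. Exit rates as high as 50% have no support in the documents. All of this stands, and it lowers the severity.

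It is also fair that bias arises only if leavers are excluded from the analysis, which is a wider gap affecting every exit route. That supports an analysis rule for all early stoppers. It does not make the item 2 wording harmless, because a reading never taken cannot be restored by an analysis rule.

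A reader might infer that the loss can only favour the drug. The documents do not support that. Only eligibility for this exit is tied to response; the direction of bias depends on later outcomes the plan does not give, and it is zero or negative in two of the four cases above. A reader might also infer that V.C deliberately chose study exit because section VII.C speaks of withdrawing medication. VII.C is a severity scale, not a follow-up rule, and does not show this.

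**Conclusion.** The point holds in a limited form. Item 2 gives a study exit only to adults without obvious improvement at month 3. No text clearly requires their month-6 or VI.C efficacy evaluations afterwards, and IV.D item 2 could remove them. The month-6 and off-drug efficacy result can therefore be overstated if leavers do worse than stayers. There is no bias if the end-of-therapy evaluation is done, used and reflects their month-6 state, or if their outcomes match those of the patients who stay.

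Neither size nor direction can be estimated from the documents; every figure above except the minimum of 10 rests on assumption. The effect is probably small against sampling error at about 10 patients. The reason to act is that the loss is cheap to prevent, not that it is known to be large. The item 1 exit follows toxicity and is not part of the response-selective problem. Severity: consider.

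**What to change.** 1. **V.C item 2.** Replace leaving the study with stopping sirolimus. Add that, unless consent is withdrawn, the patient completes the month-6 evaluation and the VI.C evaluations already planned, without repeating CT or endoscopy done shortly before.
2. **IV.D item 2 and VIII.B.** State that patients who stop the drug early by any route are not rejected as incomplete and stay in the efficacy analysis with all available readings, including month 3 and end of therapy. Counting a missing month-6 outcome as not improved is a sensitivity analysis only, for the reason in step 4 of the working.
3. **Item 1 stoppers.** Apply only this analysis rule and the existing VI.C end-of-therapy evaluation, with no added CT or endoscopy.

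The cost is a short amendment. For an item 2 stopper the month-6 reading is taken off drug, with at most one CT and endoscopy beyond the VI.C evaluations. The efficacy figure may be less favourable. No dose or drug-stopping rule changes, and the free right to withdraw in section IV.C is untouched.

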### VI. Follow-up plan and content

#### A. Evaluation before the trial

Each subject should complete the following items in four weeks before the treatment:

1) Complete medical history

2) Detailed personal profile

3) A physical examination

4) VAS pain score

5) (Patients suspected with secondary malignant lesions) tumor markers examination, including CEA, CA199 and CA125

6) (Female aged 25 or elder) ultrasonic examination of uterus and its appendages

7) Blood and urine routine examination

8) Liver and kidney function, blood lipid test

9) (Patients with secondary malignant tumor) chest CT and other related examinations

10) Abdominal and pelvic cavity contrast-enhanced CT + small intestine reconstruction CT examination

11) Digestive system endoscopy

12) (Female of childbearing age) blood/urine pregnancy test

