# IV. Selection of subjects

### A. Inclusion criteria

- (1) Patients are diagnosed with PJS.
- (2) Patients have gastrointestinal polyps related syndromes, including abdominal pain, abdominal distension, gastrointestinal bleeding, etc, with imageological

examination suggesting intestinal obstruction or intussusception; or whose symptoms recur after previous digestive system endoscopic treatment and surgery; or who are inappropriate or unwilling to accept the above treatment again and wish to receive pharmacotherapy.

- (3) Conventional treatment doesn't work well in patients with PJS-related malignant tumors.
- (4) Physical condition (ECGO): 0~3
- (5) Organ function is good and biochemical indices meet the following conditions:
  - a) AST <2.5×upper limit of normal value (ULN),
  - b) ALT <2.5×upper limit of normal value (ULN),
  - c) Serum total bilirubin (TSB)≤1.5×upper limit of normal value (ULN),
  - d) Creatinine <1.5×upper limit of normal value (ULN).
- (6) No other medications have been received for intestinal polyps within 3 months prior to the clinical trial.
- (7) Patients volunteer to participate in the trial. Participant or his/her legal guardian signs the informed consent form.

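### The only pre-treatment symptom reading may be four weeks old at first dose, so symptom change before any drug can be counted as improvement on sirolimus

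*Combined protocol and SAP*

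**What the plan says.** Inclusion criterion (2) in section IV.A offers three routes.

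- Route one is symptoms with supporting imaging: "Patients have gastrointestinal polyps related syndromes, including abdominal pain, abdominal distension, gastrointestinal bleeding, etc, with imageological", continuing to imaging that suggests obstruction or intussusception.
- Route two is recurrence: "or whose symptoms recur after previous digestive system endoscopic treatment and surgery".
- Route three is unsuitability or reluctance: "or who are inappropriate or unwilling to accept the above treatment again and wish to receive pharmacotherapy".

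Section VI.A sets the baseline: "Each subject should complete the following items in four weeks before the treatment". The list contains one VAS pain score. It asks for no repeat, run-in, stability check or reading on the day of first dose.

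Section VI.B schedules weekly contacts in the first month, for adverse reactions only. Efficacy is assessed at months 3 and 6 with the same content as the pre-trial evaluation, and the first efficacy item is "Clinical symptom assessment (including ileus, VAS pain score, gastrointestinal bleeding and some other related symptoms". Section VI.C adds evaluations at the end of therapy and 6 and 12 months later.

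Section VIII.B lists symptom improvement among the efficacy analyses. It does not define improvement or say which reading is the baseline. Section III describes the design: "This study is a prospective, nonrandomized, open-label, single-arm clinical trial".

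**The concern.** Under routes one and two, patients come in when symptoms are present, and route two itself describes symptoms that return after treatment. A group chosen in this way will tend to report milder symptoms later whether or not it is treated. If the only pre-treatment reading can be up to 28 days old, some of that easing may happen before the first dose.

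Consider a patient scored in pain on day -28, pain-free by day -3 and still pain-free at month 3. The plan's comparison shows an improvement, yet sirolimus cannot have caused it. No control arm shows the drug-free change, and no second reading shows how much came before treatment.

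What is at stake is the symptom result: VAS pain, ileus and bleeding. The pre-dose reading cannot be recovered once the first dose has been taken.

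**Working it through.** **Plan's own figures.** The only sample-size figure is "No less than 10 patients should be enrolled". No effect size, SD, response rate or power stands behind it, so there is nothing to reproduce. All numerical inputs below are assumptions, used to show scale.

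**1. What the schedule can and cannot separate.**

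| Time | Efficacy reading of symptoms |
|---|---|
| Some day in the 4 weeks before treatment | One (VI.A) |
| Day of first dose | None |
| Weekly in month 1 | None; adverse reactions only (VI.B) |
| Months 3 and 6 | Yes (VI.B) |
| End of therapy, then 6 and 12 months later | Yes (VI.C) |

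Write S for the pre-trial score, D for the score at first dose and M for the month-3 score. Then S - M = (S - D) + (D - M). The plan observes only the sum. The first bracket is drug-free by construction, but it is included in the apparent benefit.

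**2. Scale of the whole drug-free fall.** Assume a 0-10 VAS with usual mean 3, SD 2.5, entry at 4 or more, and correlation r between readings.

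- Expected fall = (1 - r) × SD × φ(z) / (1 - Φ(z))
- z = (4 - 3) / 2.5 = 0.4, and the ratio φ/(1 - Φ) is 1.069
- SD × ratio = 2.5 × 1.069 = 2.67
- r = 0.4: 0.6 × 2.67 = 1.60 points
- r = 0.6: 0.4 × 2.67 = 1.07 points
- r = 0.8: 0.2 × 2.67 = 0.53 points

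**3. The part that falls before first dose.** Suppose r = 0.8 from screening to first dose and r = 0.4 from screening to month 3. The total fall is 1.60. The pre-dose part is 0.53. The remainder, 1.60 - 0.53 = 1.07, comes after first dose and stays whichever baseline is used.

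**4. In counts.** Take 10 patients who all qualify on an episode, with no drug effect, and let p be the share whose symptoms have settled unaided by month 3, before or after first dose.

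| p (assumed) | Expected improved | Chance of at least 5 of 10 |
|---|---|---|
| 10% | 1 | 0.2% |
| 30% | 3 | 15% |
| 50% | 5 | 62% |
| 70% | 7 | 95% |

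An observed 5 of 10 has an exact 95% interval of 19% to 81%, too wide to tell these cases apart.

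**5. Simulation.** This used 10 patients, no drug effect, entry when the screening score was in the top 50% or 30%, one equal correlation of 0.3 to 0.9 between all times, and a paired t-test with nominal 2.5% in the improvement direction.

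| Baseline used | Spurious mean improvement | Trials significant for improvement |
|---|---|---|
| Screening score | 0.08 to 0.82 SD | 7.5% to 62% |
| Mean of screening and pre-dose scores | 0.04 to 0.40 SD | 4.7% to 21% |
| Pre-dose score not used for entry | about 0 SD | 2.2% to 2.7% |

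The last row depends on the equal correlations. Where the correlation fades with time, as in step 3, a residual remains. The protocol plans no such test, so the percentages are only a yardstick. They do show that the new reading must stay out of the eligibility decision, and that averaging it with the screening score only halves the shift.

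**The case against.** The case against has force on several points.

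- **Not every patient is selected on an episode.** Route three does not expressly require one. A patient who enters that way in a quiet spell can only stay level or worsen on VAS, so a reader who infers that the bias always favours the drug goes too far. It does so on average.
- **No VAS threshold exists.** The cut-off of 4 is invented for illustration, and the VAS need not be the reading that prompted entry. Recurrence may also mean persistent disease rather than a passing episode. The documents give no rate of spontaneous resolution.
- **The most acute cases are trimmed.** Section IV.B excludes patients likely to need emergency surgery soon or needing immediate transfusion. The off-treatment evaluations give a further, weak check.
- **Four-week screening windows are conventional**, and the analysis is descriptive.
- **A reader might infer that this reading drives the month-3 dose decision.** The text does not support that. The adult rule in V.C refers to the disease condition, which is undefined and need not mean symptoms; VI.B also lists hemoglobin, nutrition, polyp measures and tumor response. V.B has no equivalent rule for children.
- **A first-dose reading does not remove all the regression**, as step 3 shows.

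These points limit the reach and size of the concern. They do not remove it: no section provides a symptom reading at first dose, and change before that point is credited to treatment. A descriptive analysis is biased by the same amount as a tested one.

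**Conclusion.** The point holds for symptom outcomes (VAS pain, ileus, bleeding) in patients admitted through the first two routes. For them, drug-free change over as much as four weeks can enter the symptom-improvement result, on average in favour of sirolimus. It does not extend to CT or endoscopic measures of polyp size, number and load.

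The mechanism follows from the text, with one inference: the pre-trial reading is the comparator. VIII.B does not say so, but no other pre-treatment reading is scheduled.

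The size cannot be derived from the documents. In the illustration, 0.53 of a 1.60-point fall came before first dose; a screening visit only a few days before dosing would give less. It would be tempting to read any symptom benefit in this trial as regression to the mean. The documents do not support that, because they give neither the variability of symptoms nor the rate at which they settle.

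**What to change.** Add to VI.A a dated VAS score and a short record of pain, ileus and bleeding on the day of first dose, before the dose, not used for eligibility. This also gives ileus and bleeding a dated baseline; at present VI.A lists the VAS as its only specific symptom measure.

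In VIII.B, name this reading as the baseline for symptom change, define improvement against it, and report the change from screening to first dose beside it as the drug-free change. State as a limitation that resolution after first dose cannot be separated from a drug effect in a single arm. No change to the month-3 dose rule in V.C is proposed.

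The cost is one short questionnaire and possibly a smaller apparent symptom benefit. The protocol describes no first-dose visit, but section III already provides for remote follow-up and VI.B for an electronic diary of drug intake. Either could carry the record without a visit or scan.

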### **B.** Exclusion criteria

- (1) Patients underwent a surgery within 2 weeks.
- (2) Patients may need emergency surgery in the near future.
- (3) Patients are allergic to any ingredient of rapamycin.
- (4) Patients suffer from a disease requiring immediate blood transfusion.
- (5) Patients suffer from any disease or condition that may impact implementation of the study or interpretation of the results. This type of diseases includes:
  - a) Known severe blood coagulation disorders
  - b) Known anemia that is not caused by intestinal polyps
  - c) Known hemoglobinopathy
  - d) Other gastrointestinal infectious diseases
  - e) Serious heart, liver, kidney and other concomitant diseases that may endanger lives
- (6) Patients are in pregnancy and lactation.
- (7) Alcohol or drug (such as aperient) abuse
- (8) Patients took part in another clinical trial that may influence this study.
- (9) The researchers believe that there are other unfavorable reasons for the patient to become a subject.

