### C. Exit criteria

- (1) An allergic reaction occurs.
- (2) The patient requests withdrawal: at his or her own discretion or at the request of his or her legal representative. Subjects may refuse to participate in further studies at any time without providing reasons. Subjects will not be affected because of such decision.
- (3) Subjects are required to withdraw from the study in certain special circumstances. (eg, there is significant issues of compliance, safety, or surgery for venous malformations)
- (4) Other situations in which the study must be terminated. For example, the

investigators believe that continuing the study may be harmful to the health of subjects.

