### V. Therapeutic schedule

### A. Enrollment

Before starting the study, the investigator clearly and colloquially explains the study and its potential risks and benefits to the patient or his/her authorizer. Patient or his/her authorizer and the investigator sign and date the informed consent form. Only after signing the informed consent form can patient or his/her authorizer enter the screening section and then participate in the study. Patients who sign a written informed consent need to be assessed to determine if the patient meets the study criteria:

1) Demographic data and medical history of the patient;

2) vital signs;

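### The baseline pregnancy test may be up to 28 days old at first dose, so a pregnancy that becomes detectable after it may go unnoticed when sirolimus starts

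*Combined protocol and SAP*

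**What the plan says.** Section IV.B, exclusion (6), bars women who are pregnant or breast-feeding: "Patients are in pregnancy and lactation". It does not say how or when this is confirmed.

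Section VI.A lists twelve baseline items under one timing rule: "Each subject should complete the following items in four weeks before the treatment". Item 12 is the pregnancy test: "Female of childbearing age) blood/urine pregnancy test". Item 6 is a pelvic ultrasound limited by age: "Female aged 25 or elder) ultrasonic examination of uterus and its appendages". Neither has a window of its own.

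Section VI.B brings the pregnancy test back on treatment only by cross-reference. Efficacy and safety are "evaluated at the 3rd and 6th months, and the contents of the examination is the same as the pre-trial evaluation". The same section provides for weekly review of adverse reactions in the first month and for regular safety monitoring throughout. Neither provision lists a pregnancy test.

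Section V.A introduces the eligibility assessment: "Patients who sign a written informed consent need to be assessed to determine if the patient meets the study criteria". In our copy, the list that follows has two entries (history and vital signs) and ends on a semicolon.

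**The concern.** The exclusion is meant to protect at the first dose, but the test that supports it can be four weeks old by then. That window suits CT and endoscopy, which are hard to schedule and whose findings change slowly. Pregnancy status can change within it. A woman tested on day -28 can be negative, become detectably pregnant before day 0, and start daily sirolimus without any visible rule calling for another look.

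The documents themselves treat this as important. They exclude pregnancy, test for it, count congenital malformation as a serious adverse event (section VII.A), and acknowledge that the drug is used outside its indication (section XI). What is at stake is avoidable early exposure in an individual woman, not the validity of the results.

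**Working it through.** The plan states no figure on this point, so there is none to reproduce. The check is date arithmetic followed by an illustration on assumed inputs.

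**Inputs from the protocol**
- Baseline window: four weeks = 4 × 7 = 28 days (VI.A).
- Next scheduled test: month 3 (VI.B), taken here as 91 days after the first dose.
- Other pre-dose pregnancy tests in the visible text: none.

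**Age of the test and length of the gap**

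| | Oldest test at first dose | Longest gap to month-3 test |
|---|---|---|
| As written | 28 days | 28 + 91 = 119 days |
| With a 7-day rule | 7 days | 7 + 91 = 98 days |

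The longest gap shortens by (119 − 98)/119 = 17.6%. If test dates are spread evenly over the window, the mean age of the test is 14 days as written and 3.5 days under the rule. The mean gap then goes from 14 + 91 = 105 to 3.5 + 91 = 94.5 days, which is 10% shorter.

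**Expected number of cases**

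The documents give neither the number of women of childbearing age nor a pregnancy rate; section III sets only a minimum of 10 patients, and children may take part. Assumptions: 5 such women, and 2-10% pregnancies per woman-year at a constant rate.

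Expected pregnancies becoming detectable between test and first dose = women × yearly rate × days/365.

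- All tested on day -28: 5 × 0.02 × 28/365 = 0.0077, up to 5 × 0.10 × 28/365 = 0.0384.
- All tested on day -7: 5 × 0.02 × 7/365 = 0.0019, up to 5 × 0.10 × 7/365 = 0.0096.
- Avoided, worst case (21 days): 0.0058 to 0.0288.
- Avoided, dates spread evenly (14 − 3.5 = 10.5 days): 0.0029 to 0.0144.

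Varying the number of women, still in the worst case: 3 women at 2% give 3 × 0.02 × 21/365 = 0.0035, and 10 women at 10% give 10 × 0.10 × 21/365 = 0.0575.

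**Do the other provisions close the gap?**
- The ultrasound could show a pregnancy, but it shares the 28-day window, is required only from age 25, and is not described as a pregnancy check.
- The weekly month-1 reviews and the regular safety monitoring may bring a pregnancy to light, but they come after dosing has begun and schedule no test.
- Exit criterion (4) applies where the "investigators believe that continuing the study may be harmful to the health of subjects". It lets the investigator act once a pregnancy is known; it does not find one.

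**The case against.** **The text may be incomplete.** The list in V.A appears cut off and the consent pages were removed. A second screening check or a contraception rule could stand in either place. A reader might infer that the protocol has no later check at all; the documents do not support that. What stands is narrower: the window stated in VI.A is 28 days, and no visible text tightens it.

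**Exclusion (6) bars pregnancy itself, not a positive test.** A reader might infer that the plan treats a pregnant woman as eligible if her day -28 test was negative. It does not: she is ineligible, but her ineligibility may not be detected. Exclusion (9) also lets the researchers refuse a patient for other reasons. This objection is right, and the point is confined to detection.

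**Exposure until month 3 is a worst case.** A pregnancy that becomes detectable shortly before dosing may well show itself in the first weeks on drug, when contact is weekly. A reader might infer three months of exposure as the expected course; the text supports it only as an upper limit where nothing is noticed earlier.

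**The yield is small and the larger interval is untouched.** On the same assumptions, the 91 treatment days before month 3 carry 5 × 0.02 × 91/365 = 0.025 to 5 × 0.10 × 91/365 = 0.125 pregnancies, about four times what the rule removes in the worst case (91/21 = 4.3). That is correct. But those would begin after a valid start, whereas this point concerns whether an existing exclusion works at the first dose.

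**Seven days is a judgement.** Nothing in the documents favours 7 over 14, and no test finds a very recent conception. Both are true. The argument is for moving the test close to the first dose; 7 days is a practical limit.

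**Conclusion.** The point holds as a modest, inexpensive safety improvement. The visible plan accepts a negative pregnancy test up to 28 days old at first dose, so a pregnancy that becomes detectable in that interval may go unnoticed although exclusion (6) bars it.

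The 28 days follow directly from VI.A; they are the permitted maximum, not the typical interval. The case count rests wholly on the assumed number of women, pregnancy rate and spread of test dates. Across the two test-date scenarios, with 5 women, a 7-day rule avoids about 0.003 to 0.03 cases in the trial. Sample size, endpoints and analysis are unaffected, and it would be wrong to read this as a flaw that threatens the trial. Certainty is limited by the parts of the text that we cannot see.

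**What to change.** In VI.A, take item 12 out of the four-week window and give it its own timing, for example:

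> Women of childbearing age: negative blood or urine pregnancy test within 7 days before, or on the day of, the first dose. Exclusion (6) is checked against this result before the drug is started.

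The visible text describes no on-site visit for the first dose, and section III says "Patients are followed up remotely in a regular schedule". A home urine test confirmed with the investigator should therefore be acceptable, with a short note on how it is confirmed and recorded.

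The cost is one line of text and at most one extra urine test or short attendance per woman of childbearing age. If a later check already stands in the full enrolment list or the consent form, a cross-reference in VI.A is enough.
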